3 DF/HCC REQUIREMENTS FOR MULTI-CENTER PROTOCOLS

Certain DF/HCC Policy requirements apply to External Sites participating in DF/HCC research. The following section will clarify DF/HCC requirements and further detail the expectations for participating in a DF/HCC Multi-Center protocol.

3.1 Protocol Revisions and Closures

The External Sites will receive notification of protocol revisions and closures from the Coordinating Center. When under a separate IRB, it is the individual External Site's responsibility to notify its IRB of these revisions.

- **Protocol revisions:** External Sites will receive written notification of protocol revisions from the Coordinating Center. All protocol revisions must be IRB approved and implemented within a timely manner from receipt of the notification.
- **Protocol closures and temporary holds:** External Sites will receive notification of protocol closures and temporary holds from the Coordinating Center. Closures and holds will be effective immediately. In addition, the Coordinating Center, will update the Participating Institutions on an ongoing basis about protocol accrual data so that they will be aware of imminent protocol closures.

3.2 Informed Consent Requirements

The DF/HCC approved informed consent document will serve as a template for the informed consent for External Sites. The External Site consent form must follow the consent template as closely as possible and should adhere to specifications outlined in the DF/HCC Guidance

Document on Model Consent Language for Investigator-Sponsored Multi-Center Trials. This document will be provided separately to each External Site upon request.

External Sites are to send their version of the informed consent document to the Coordinating Center for review and approval prior to submission to their local IRB. The approved consent form must also be submitted to the Coordinating Center after approval by the local IRB for all consent versions.

The Principal Investigator (PI) at each External Site will identify the physician members of the study team who will be obtaining consent and signing the consent form for therapeutic protocols. External Sites must follow the DF/HCC requirement that for all interventional drug, biologic, or device research, only attending physicians may obtain initial informed consent and any re-consent that requires a full revised consent form.

3.3 IRB Re-Approval

Verification of IRB re-approval from the External Sites is required in order to continue research activities. There is no grace period for continuing approvals.

The Coordinating Center will not register participants if a re-approval letter is not received from the Participating Institution on or before the anniversary of the previous approval date.

3.4 DF/HCC Multi-Center Protocol Confidentiality

All documents, investigative reports, or information relating to the participant are strictly confidential. Whenever reasonably feasible, any participant specific reports (i.e. Pathology Reports, MRI Reports, Operative Reports, etc.) submitted to the Coordinating Center should be de-identified. It is recommended that the assigned protocol case number (as described below) be used for all participant specific documents. Participant initials may be included or retained for cross verification of identification.

3.5 Participant Registration

3.5.1 Participant Registration

To register a participant, the following documents should be completed by the External Site and e-mailed to the Coordinating Center:

[name]
Dana-Farber Cancer Institute
[name]
[name]
Email: [contact]
[contact]

- Signed participant consent form
- HIPAA authorization form
- DFCI eligibility checklist
- Screening provider note including the medical/surgical history, ECOG performance status, vital signs, and physical exam findings
- Copies of laboratory reports and clinical information confirming satisfaction of eligibility criteria.

The Coordinating Center will review the submitted documents in order to verify eligibility and consent. To complete the registration process, the Coordinating Center will:

- Register the participant on the study with the DF/HCC Clinical Trial Management System (CTMS).
- Upon receiving confirmation of registration, the Coordinating Center will inform the External Site and provide the study specific participant case number, and if applicable, assigned treatment and/or dose level.

At the time of registration, the following identifiers are required for all subjects: initials, date of birth, gender, race and ethnicity. Once eligibility has been established and the participant successfully registered, the participant is assigned a unique protocol case number. External Sites should submit all de-identified subsequent communication and documents to the Coordinating Center, using this case number to identify the subject.

3.5.2 Initiation of Therapy

Participants must be registered with the DF/HCC CTMS before the initiation of treatment or other protocol-specific interventions. Treatment and other protocol-specific interventions may not be initiated until the External Site receives confirmation of the participant's registration from the Coordinating Center. The DF/HCC Sponsor and DFCI IRB must be notified of any violations to this policy.

3.5.3 Eligibility Exceptions

No exceptions to the eligibility requirements for a protocol without DFCI IRB approval will be permitted. All External Sites are required to fully comply with this requirement. The process for requesting an eligibility exception is defined below.

3.6 Data Management

DF/HCC develops case report forms (CRF/eCRFs), for use with the protocol. These forms are designed to collect data for each study. DF/HCC provides a web-based training for all eCRF users.

3.6.1 Data Forms Review

Data submissions are monitored for timeliness and completeness of submission. If study forms are received with missing or questionable data, the submitting institution will receive a written or electronic query from the DF/HCC Office of Data Quality, Coordinating Center, or designee.

Responses to all queries should be completed and submitted within **14 calendar days**.

If study forms are not submitted on schedule, the External Site will periodically receive a Missing Form Report from the Coordinating Center noting the missing forms.

3.7 Protocol Reporting Requirements

3.7.1 Protocol Deviations, Exceptions and Violations

Federal Regulations require an IRB to review proposed changes in a research activity to ensure that researchers do not initiate changes in approved research without IRB review and approval, except when necessary to eliminate apparent immediate hazards to the participant. DF/HCC requires all departures from the defined procedures set forth in the IRB approved protocol to be reported to the DF/HCC Sponsor and to the IRB of record.

3.7.2 Reporting Procedures

Requests to deviate from the protocol require approval from the IRB of record and the sponsor.

All protocol violations must be sent to the Coordinating Center in a timely manner. The Coordinating Center will provide training for the requirements for the reporting of violations.

3.7.3 Guidelines for Processing IND Safety Reports

The DF/HCC Sponsor will review all IND Safety Reports per DF/HCC requirements and ensure that all IND Safety Reports are distributed to the External Sites as required by DF/HCC Policy. External Sites will review/submit to the IRB according to their institutional policies and procedures.

4 MONITORING: QUALITY CONTROL

The Coordinating Center, with the aid of the DF/HCC Office of Data Quality, provides quality control oversight for the protocol.

4.1 Ongoing Monitoring of Protocol Compliance

The External Sites may be required to submit participant source documents to the Coordinating Center for monitoring. External Sites may also be subject to on-site monitoring conducted by the Coordinating Center.

The Coordinating Center will implement ongoing monitoring activities to ensure that External Sites are complying with regulatory and protocol requirements, data quality, and participant safety. Monitoring practices may include but are not limited to; source data verification, and review and analysis of eligibility requirements, informed consent procedures, adverse events and all associated documentation, review of study drug administration/treatment, regulatory files, protocol departures reporting, pharmacy records, response assessments, and data management.

External Sites will be required to participate in regular Coordinating Center initiated teleconferences.

Remote Monitoring: External Sites will be required to forward de-identified copies of participants' medical record and source documents to the Coordinating Center to aid in source data verification.

and/or

On-Site Monitoring: Source documentation verification (SDV) will be conducted yearly by having access to participants' complete medical record and source documents.

4.2 Monitoring Reports

The DF/HCC Sponsor will review all monitoring reports to ensure protocol compliance. The DF/HCC Sponsor may increase the monitoring activities at External Sites that are unable to comply with the protocol, DF/HCC Sponsor requirements or federal and local regulations.

4.3 Accrual Monitoring

Prior to extending a protocol to an external site, the DF/HCC Sponsor will establish accrual requirements for each External Site. Accrual will be monitored for each External Site by the DF/HCC Sponsor or designee. Sites that are not meeting their accrual expectations may be subject to termination. Minimum site accrual expectations have been set to 3 subjects per year.

5 AUDITING: QUALITY ASSURANCE

5.1 DF/HCC Internal Audits

All External Sites are subject to audit by the DF/HCC Office of Data Quality (ODQ). Typically, approximately 3-4 participants would be audited at the site over a 2-day period. If violations which impact participant safety or the integrity of the study are found, more participant records may be audited.

5.2 Audit Notifications

It is the External Site's responsibility to notify the Coordinating Center of all external audits or inspections (e.g., FDA, EMA, NCI) that involve this protocol. All institutions will forward a copy of final audit and/or re-audit reports and corrective action plans (if applicable) to the Coordinating Center, within 12 weeks after the audit date.

5.3 Audit Reports

The DF/HCC Sponsor will review all final audit reports and corrective action plans, if applicable. The Coordinating Center must forward any reports to the DF/HCC ODQ per DF/HCC policy for review by the DF/HCC Audit Committee. For unacceptable audits, the DF/HCC Audit Committee would forward the final audit report and corrective action plan to the DFCI IRB as applicable.

5.4 External Site Performance

The DF/HCC Sponsor and the IRB of record are charged with considering the totality of an institution's performance in considering institutional participation in the protocol.

External Sites that fail to meet the performance goals of accrual, submission of timely and accurate data, adherence to protocol requirements, and compliance with state and federal regulations, may be put on hold or closed.

APPENDIX D: NEW YORK HEART ASSOCIATION CLASSIFICATION

Class	Functional Capacity	Objective Assessment
I	Patients with cardiac disease but without resulting limitations of physical activity. Ordinary physical activity does not cause undue fatigue, palpitation, dyspnea, or anginal pain.	No objective evidence of cardiovascular disease.
II	Patients with cardiac disease resulting in slight limitation of physical activity. They are comfortable at rest. Ordinary physical activity results in fatigue, palpitation, dyspnea, or anginal pain.	Objective evidence of minimal cardiovascular disease.
III	Patients with cardiac disease resulting in marked limitation of physical activity. They are comfortable at rest. Less than ordinary activity causes fatigue, palpitation, dyspnea, or anginal pain.	Objective evidence of moderately severe cardiovascular disease.
IV	Patients with cardiac disease resulting in inability to carry on any physical activity without discomfort. Symptoms of heart failure or the anginal syndrome may be present even at rest. If any physical activity is undertaken, discomfort is increased.	Objective evidence of severe cardiovascular disease.

Source: The Criteria Committee of New York Heart Association. Nomenclature and Criteria for Diagnosis of Diseases of the Heart and Great Vessels. 9th Ed. Boston, MA: Little, Brown & Co; 1994:253-256.

APPENDIX E: IWCLL 2018 HEMATOLOGIC TOXICITY GUIDELINES

Table 26: Grading Scale For Hematological Toxicity in CLL Studies¹		
Grade²	Decrease in platelets³ or hemoglobin⁴ (nadir) from baseline value, %	Absolute neutrophil count (nadir)⁵ × 10⁹/L
0	No change to 10	≥ 2
1	11 – 24	≥ 1 and < 2
2	25 – 49	≥ 1 and < 1
3	50 – 74	≥ 0.5 and < 1
4	≥ 75	< 0.5

1. Refer to iwCLL 2018 Criteria¹
2. Grades: 1, mild; 2, moderate; 3, severe; 4, life-threatening; 5, fatal. Death occurring as a result of toxicity at any level of decrease from baseline will be recorded as grade 5.
3. Platelet counts must be below normal levels for grades 1-4. If, at any level of decrease the platelet count is $<20 \times 10^9/L$, this will be considered grade 4 toxicity unless a severe or life-threatening decrease in the initial platelet count (e.g., $20 \times 10^9/L$) was present at baseline, in which case the patient is not evaluable for toxicity referable to platelet counts.
4. Hb levels must be below normal levels for grades 1-4. Baseline and subsequent Hb determinations must be performed before any given transfusions. The use of erythropoietin is irrelevant for the grading of toxicity but should be documented.
5. If the absolute neutrophil count (ANC) reaches $<1 \times 10^9/L$, it should be judged to be grade 3 toxicity. Other decreases in the white blood cell count or in circulating granulocytes are not to be considered because a decrease in the white blood cell count is a desired therapeutic end point. A gradual decrease in granulocytes is not a reliable index in CLL for stepwise grading of toxicity. If the ANC was $<1 \times 10^9/L$ before therapy, the patient is not evaluable for toxicity referable to the ANC. The use of G-CSF is irrelevant for the grading of toxicity but should be documented.

APPENDIX F: ACALABRUTINIB DRUG DIARY

Study Participant Self-Administration Instructions

The study staff will explain how to take acalabrutinib, but these are points to remember:

1. Take the drug twice daily approximately 12 hours apart.
2. Take the drug with about 8 ounces of water. Acalabrutinib can be taken with or without meals.
3. You may **NOT** consume: Grapefruit or grapefruit products, Seville oranges (including marmalade containing Seville oranges) or starfruit within the 3-day period prior to the first study drug administration and until the last day of treatment is completed due to possible CYP3A mediated metabolic interaction.
4. If you miss taking your dose at the scheduled time, it can be taken as soon as possible up to 3 hours after the scheduled time. If a dose is missed by more than 3 hours, it should be skipped, and the next dose should be taken at its regularly scheduled time. Please make sure to record the reason for missing the dose. If you vomit a dose, do not take it again unless you can see the capsule.
5. Please remember to bring your study drug supply, including empty bottles and remaining pills, and drug diary with you to your clinic appointment. Please do not throw away any empty bottles. On clinic days please take your study medication on your regular schedule.
6. If you are taking a H2 receptor antagonist, then it should be taken approximately 2 hours after an acalabrutinib dose.
7. The drug can be stored at room temperature.
8. Keep this drug out of the reach of children.

Please call your doctor or research nurse before taking any new prescription or over-the-counter medications/supplements other than the study drugs or if any other questions arise.

Study Participant Self-Administration Diary for Acalabrutinib

Please record how many tablets you take and the time you take them and bring the completed diary as well as your study drug supply, including empty bottles, to every study visit. This will help us keep track of your study drug and how well you are tolerating it.

Participant Identifier: _____

Cycle Number: _____

Protocol #: _____

Study Doctor: _____

Study Nurse: _____

Contact Number: _____

You will take the following number of tablets each time (per dose) as listed in the table below:

Study Drug Name	# of tablets to take per dose	# of times each day
Acalabrutinib		

FOR STUDY TEAM USE ONLY	
Staff initials:	
Date dispensed:	Date returned:
# pills/caps/tabs dispensed:	# pills/caps/tabs returned:

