4. TREATMENT PLAN

4.1 Treatment Regimen

A treatment cycle is defined as 28 consecutive days. Treatment will be administered on an outpatient basis. Reported adverse events and potential risks are described in **Section 7**. Appropriate dose modifications are described in **Section 6**.

Participants will receive acalabrutinib at the FDA approved dose of 100 mg by mouth twice daily and umbralisib at 800 mg by mouth once daily continuously throughout each treatment cycle. Ublituximab will be given IV starting with cycle 7 on days 1, 2, 8, and 15 and cycles 8-12 on day 1.

Participants who are in bone marrow and CT confirmed CR at the end of cycle 12 will stop dosing with acalabrutinib and umbralisib.. Participants not in CR will continue to cycles 13-24.

Participants will have peripheral blood monitoring for MRD as described in the **Study Calendar** in **Section 10**. If early relapse or recurrence is detected, the patient will undergo restaging with a CT scan and a bone marrow biopsy / aspirate. At the discretion of the treating investigator, patients with early relapse not meeting iwCLL criteria for retreatment may resume dosing with acalabrutinib and umbralisib until further disease progression, unacceptable toxicity, or other criteria are met as described in **Section 5.5**. The study agents will be resumed at the dose levels the participant was receiving prior to discontinuation. Dosing will resume for a maximum of 12 additional treatment cycles, such that participants may receive a maximum total of 36 cycles of study therapy.

Table 4: Regimen Description

Agent	Premedications; Precautions	Dose	Route	Schedule ¹	Cycle Length
Acalabrutinib	May be taken with or without food.	100 mg	By mouth	Twice Daily	
Umbralisib	Take within 30 minutes of a meal. Participants are required to receive prophylactic anti-viral and anti-pneumocystis jiroveci pneumonia (PJP) treatment, refer to Section 5.4 .	800 mg	By mouth	Once Daily	28 days

Table 4: Regimen Description

Agent	Premedications; Precautions	Dose	Route	Schedule ¹	Cycle Length

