4.5 Criteria for Taking a Participant Off Protocol Therapy

Duration of therapy will depend on individual response, evidence of disease progression and tolerance. In the absence of treatment delays due to adverse event(s), treatment may continue for a maximum of 24 cycles or until one of the following criteria applies:

- Disease progression, with the exception of participants who relapse following confirmed CR and treatment discontinuation who are permitted to be re-treated as described in **Section 5.1**
- Intercurrent illness that prevents further administration of treatment
- Unacceptable adverse event(s)
- Participant becomes pregnant or plans to become pregnant
- Participant demonstrates an inability or unwillingness to comply with the oral medication regimen and/or documentation requirements
- Participant decides to withdraw from the protocol therapy
- General or specific changes in the participant's condition render the participant unacceptable for further treatment in the judgment of the treating investigator

Participants will be removed from the protocol therapy when any of these criteria apply. The reason for removal from protocol therapy, and the date the participant was removed, must be documented in the case report form (CRF). Alternative care options will be discussed with the participant.

When a participant is removed from protocol therapy and/or is off of the study, the participant's status must be updated in OnCore in accordance with [REGIST-OP-1](#).

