5.2 Dose Modifications

Permitted dose reductions of acalabrutinib and umbralisib are detailed below. Once a participant's dose has been reduced due to toxicity, it may not be re-escalated. If a subject requires a dose reduction of umbralisib and further evaluation of the toxicity reveals the event was not related to umbralisib, this should be recorded in the medical record and dose re-escalation to the previous umbralisib dose may be considered at the discretion of the treating investigator after consultation with the sponsor-investigator. No dose reductions of ublituximab are permitted. If the participant cannot tolerate the dose of ublituximab, ublituximab should be discontinued.

If attribution of the toxicity is known, dose reductions may occur independently of each other. For example, the dose of umbralisib may be reduced while maintaining the dose of acalabrutinib. If toxicity attribution is unknown or the combination of study agents may contribute to the toxicity, both agents must be dose reduced.

Table 9: Umbralisib Dose Reductions	
Dose Reduction Level	Umbralisib Dose (Once Daily)
-1	600 mg
-2	400 mg
-3	Discontinue

Table 10: Acalabrutinib Dose Reductions ^{1,2}	
Dose Reduction Level	Acalabrutinib Dose
-1	100 mg once daily
-2	Discontinue
1. Dose modifications of acalabrutinib may be made in	

Table 10: Acalabrutinib Dose Reductions ^{1,2}	
Dose Reduction Level	Acalabrutinib Dose
accordance with the FDA prescribing information. 2. Refer to Section 5.4 for dose modifications for co-administered CYP3A drugs.	

If attribution of the toxicity is known, discontinuation of study medications may also occur independently of each other with agreement from the sponsor-investigator. For example, participants who cannot tolerate ublituximab may be allowed to continue to receive umbralisib and acalabrutinib if the sponsor-investigator provides approval.

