# pills/caps/tabs that should have been taken:	
Discrepancy Notes:	

Day	Date	Number of Acalabrutinib tablets	Time of First Dose each day	Number of Acalabrutinib tablets	Time of Second Dose each day
1			_____:_____  Dose Not Taken Why:_____		_____:_____  Dose Not Taken Why:_____
2			_____:_____  Dose Not Taken Why:_____		_____:_____  Dose Not Taken Why:_____
3			_____:_____  Dose Not Taken Why:_____		_____:_____  Dose Not Taken Why:_____
4			_____:_____  Dose Not Taken Why:_____		_____:_____  Dose Not Taken Why:_____
5			_____:_____  Dose Not Taken Why:_____		_____:_____  Dose Not Taken Why:_____
6			_____:_____  Dose Not Taken Why:_____		_____:_____  Dose Not Taken Why:_____
7			_____:_____  Dose Not Taken Why:_____		_____:_____  Dose Not Taken Why:_____
8			_____:_____  Dose Not Taken Why:_____		_____:_____  Dose Not Taken Why:_____
9			_____:_____  Dose Not Taken Why:_____		_____:_____  Dose Not Taken Why:_____
10			_____:_____  Dose Not Taken Why:_____		_____:_____  Dose Not Taken Why:_____
11			_____:_____  Dose Not Taken Why:_____		_____:_____  Dose Not Taken Why:_____
12			_____:_____  Dose Not Taken Why:_____		_____:_____  Dose Not Taken Why:_____
13			_____:_____  Dose Not Taken Why:_____		_____:_____  Dose Not Taken Why:_____
14			_____:_____  Dose Not Taken Why:_____		_____:_____  Dose Not Taken Why:_____
15			_____:_____  Dose Not Taken Why:_____		_____:_____  Dose Not Taken Why:_____
16			_____:_____  Dose Not Taken Why:_____		_____:_____  Dose Not Taken Why:_____

Day	Date	Number of Acalabrutinib tablets	Time of First Dose each day	Number of Acalabrutinib tablets	Time of Second Dose each day

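### The acalabrutinib diary's fixed twice-daily instruction and second-dose columns contradict the once-daily schedules in Tables 8 and 10 and, for those participants, the diary's own fill-in frequency

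*Combined protocol and SAP*

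**What the plan says.** The starting schedule is in 4.1 Treatment Regimen: "Participants will receive acalabrutinib at the FDA approved dose of 100 mg by mouth twice daily". Two other places prescribe a once-daily schedule. Table 10 in 5.2 sets level -1 at "100 mg once daily", and its next level is discontinuation. Table 8 in 4.4.3 gives the same once-daily schedule with a moderate CYP3A4 inhibitor. The other two rows of Table 8 differ: a hold for short-term use of a strong inhibitor, and 200 mg twice daily with a strong inducer that cannot be avoided.

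Appendix F is the participant's form. It opens with "The study staff will explain how to take acalabrutinib, but these are points to remember", and item 1 of the list that follows is "Take the drug twice daily approximately 12 hours apart". Further down it says "You will take the following number of tablets each time (per dose) as listed in the table below". In the template that table is blank for tablets per dose and for the number "of times each day". The daily log then prints, for each of 28 days, a first-dose entry and a second-dose entry headed "Time of Second Dose each day". Each entry has a box to tick if the dose was not taken and a line for the reason.

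**The concern.** Item 1 and the log grid are written for the starting schedule, but the form is not limited to it. The contents list shows no other acalabrutinib diary. A participant moved to a once-daily schedule would therefore hold a form that says twice daily in print, once daily in the staff entry, and twice daily again in the log layout.

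The situation is foreseeable. Tables 11 and 12 in 5.3 call for an acalabrutinib reduction after certain recurrent toxicities. Under 5.2, a dose reduced for toxicity is not raised again, so the conflict would recur each remaining cycle. Under 5.5, participants still on treatment after the March 2023 withdrawal of the other two agents may continue acalabrutinib, so the form stays in use.

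What is at stake is the instruction given to people whose dose was lowered because of toxicity or an interacting drug. Section 6.4.2 requires incorrect administration to be noted on the case report form, so an unclear diary could itself produce such events.

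**Working it through.** The plan states no figure on this point, so there is none to reproduce. The check compares the daily dose under each reading of the diary.

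**Inputs**
- Tablet strength: 100 mg of acalabrutinib (7.1.2 Form).
- Frequency under item 1: 2 per day (Appendix F).
- Frequency under the completed table: whatever staff enter (Appendix F).
- Prescribed schedules: 4.1, Table 8 and Table 10.
- Diary length: 28 days, one cycle.

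**Formula**

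Daily dose = tablets per dose × 100 mg × times per day.

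| Situation | Prescribed | Item 1 followed | Completed table followed |
|---|---|---|---|
| Starting dose (4.1) | 1 × 100 × 2 = 200 mg/day | 200 mg/day, ratio 1.0 | 200 mg/day, ratio 1.0 |
| Table 10, level -1 | 1 × 100 × 1 = 100 mg/day | 1 × 100 × 2 = 200 mg/day, ratio 2.0 | 100 mg/day, ratio 1.0 |
| Table 8, moderate inhibitor | 1 × 100 × 1 = 100 mg/day | 1 × 100 × 2 = 200 mg/day, ratio 2.0 | 100 mg/day, ratio 1.0 |
| Table 8, strong inducer | 2 × 100 × 2 = 400 mg/day | 400 mg/day with two tablets entered, ratio 1.0 | 400 mg/day, ratio 1.0 |
| Table 8, short-term strong inhibitor | hold, 0 mg/day | no frequency applies | no frequency applies |

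The conflict is confined to two rows, where the ratio is 2.0 under one reading of the form and 1.0 under the other. If item 1 were followed on every day of a cycle, the excess would be 28 × (2 - 1) = 28 tablets. That is an upper bound per cycle.

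**How many people would hold such a form.** The documents give no rate of dose reduction or of moderate-inhibitor use. If 5% to 20% of the 60 planned participants were affected (an assumption), the number would be 0.05 × 60 = 3 to 0.20 × 60 = 12. This counts people given a contradictory diary, not dosing errors.

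**Comparison with the umbralisib diary.** Appendix G prints once daily, and the starting dose and both reduced levels in Table 9 are once daily. The mismatch is specific to Appendix F.

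**The case against.** The strongest reply is that the form already carries the individual schedule. Staff explain the dosing, the participant is directed to a table that staff complete, and that table has its own frequency field. The diary is issued by cycle, names a nurse and a contact number, and invites questions. Tablets dispensed and returned are counted. Item 1 repeats the standard schedule of 4.1 and 4.3.1, which is the right default for most participants.

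Most of this stands, and it limits the claim. A participant who follows the completed table takes the prescribed dose. It does not remove the contradiction, because the form never says that the table overrides item 1, and the log reinforces item 1 on every row. The opening line presents the printed list as what to remember at home, and the first item on that list disagrees with the prescription for these participants.

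A reader might also infer that a once-daily participant would appear only half adherent, with 28 of 56 dose entries used. The documents do not support that. Staff enter the number of tablets that should have been taken and any discrepancy notes, and no section computes adherence from empty log entries.

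Nor do they support a risk of removal under 4.5. That criterion reads "Participant demonstrates an inability or unwillingness to comply with the oral medication regimen and/or documentation requirements", and a participant taking the schedule the site prescribed is complying.

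**Conclusion.** The point holds as a contradiction on a participant-facing form. Item 1 and the second-dose columns of Appendix F are not conditioned on dose level. They conflict with Table 10 level -1, with the moderate-inhibitor row of Table 8, and with the diary's own frequency field once it is completed for either schedule. The possible consequence is twice the prescribed daily amount, 200 against 100 mg/day. That requires the participant to follow the printed line over the staff entry.

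Two stronger readings should be avoided. One is that any reduced participant who follows the diary necessarily doubles the dose; the completed table is also part of the diary and gives the prescribed amount. The other is that the protocol's CYP3A adjustments in general are once daily; only one of the three rows in Table 8 is.

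No endpoint, sample size or error rate is affected, and nothing here judges which schedule is clinically right. The point is worth correcting because it concerns the dosing instruction itself, in people whose dose was lowered for a safety reason.

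**What to change.** Reconcile Appendix F with Tables 8 and 10 in two steps.

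1. Replace the fixed frequency in item 1 with a direction to take the number of tablets, and the number of doses per day, that staff have written in the table on the form. State that this table governs. Make the 12-hour spacing advice apply only when the entry is twice daily.
2. When the prescribed schedule is once daily, have staff strike out the second-dose columns before issuing the diary, or supply a version with one dose entry per day.

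No dose or schedule in the protocol changes. The cost is a revision of one form and IRB approval of it, with no extra participants, visits or data.
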